After localizer scans, subjects will undergo 3 scans: 1) BOLD-weighted fMRI (EPI, TR=800 ms, FOV=23, slice=2.4mm, 96x96 matrix) for the n-back task (8 minutes); 2) BOLD-weighted resting state scan for 10 minutes to obtain data for functional connectivity analyses (eyes open, looking at fixation cross); 3) pseudo-continuous ASL (pCASL) sequence following the recommendations of the ISMRM consensus(75). Our pCASL implementation will use a 3D stack of spirals acquisition(76) with 6 interleaves (TR=5000 ms, TE=4 ms, BW=125kHz, FOV=22 cm) preceded by a 1800 ms labeling period and an 1800 ms delay to allow the label spins to clear the arteries and enter the capillary/tissue compartment. Two hyperbolic secant inversion pulses at 600 and 1300 ms after labeling will suppress background signals, after first 2 frames to permit collection of spin density images for quantification. We will acquire 20 pCASL control-label image pairs, which will be reconstructed to a 128x128 matrix. Since the excitatory effects of iTBS have been demonstrated to last up to 60 minutes,(30) data acquisitions will occur in the appropriate time frame to capture iTBS effects. The last scan in the sequence will be a high-resolution structural scan (SPGR) for image normalization, as well as a T1 scan in the same prescription as the BOLD scans to facilitate normalization.

The scans and acquisition parameters described here are representative of what will be employed, although the actual acquisitions may differ slightly. Power-monitoring software on the scanner will ensure total energy delivered to the subject will remain within FDA guidelines. Specifically, the specific absorption rate (SAR) will be not greater than: 1) 4 W/kg averaged over the whole body for any period of 15 minutes; 2) 3 W/kg averaged over the head for any period of 10 minutes; 3) 8 W/kg in any gram of tissue in the head or torso; 4) 12 W/kg in any gram of tissue in the extremities, for any period of 5 minutes.

6.2.3 Visit 2 TMS session: This session will follow the MRI session for visit 2.

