any frame with FD > 0.5 mm from the regression analysis described below, yielding a scrub ratio for each subject. As it has been demonstrated that as many as 60% of frames can be removed and still yield analyzable results,(88, 89) we will use 60% deleted frames as a cutoff for analyzable subjects. Three-compartment segmentation of the high-resolution structural image from the VBM8 normalization will be applied to the functional time series to extract cerebral spinal volume (CSF) and white matter (WM) compartments, which will be subjected to a principal component analysis to identify the top 5 components in each,(90) which corresponds to heart rate and respiratory effects on the blood oxygenation level-dependent signal.(91) Adjusted time courses will be derived from sequential regressions of the time series with the following: Linear trend, 6 motion parameters, their temporal derivatives, the quadratics of these 12 parameters, 5 components from the PCA of CSF, 5 components of PCA of WM, followed by band pass filtering from 0.01 – 0.1 Hz, and then motion scrubbing. ICA-AROMA will be used to de-noise the data and remove additional, residual motion artifacts.(92) Global signal regression (GSR) will not be done because of concerns about non-uniform transformation of correlations introduced by GSR, problematic for group comparisons.(93) For the primary analysis, the time-course from a 6 mm radius sphere at the site of stimulation will be entered into the multiple regression and correlated with every other gray-matter voxel time-course in the brain for each subject. Correlation coefficients are Z-transformed and then entered into the second level, between-subject analyses as two-sided, paired t-tests to compare between sessions. Statistical inference will be controlled as above.

(H1.2) iTBS to dlPFC, compared to vertex stimulation, will increase FPN connectivity during resting state BOLD. Because TMS effects are observed away from the site of stimulation,(38-41) we are testing functionally-defined FPN networks. We recognize that the FPN defined by n-back will not be identical to the FPN defined by a dlPFC seed-based connectivity, although the two significantly overlap.

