Exploratory analysis, amplitude of low frequency fluctuations (ALFF): ALFF, and fractional ALFF (fALFF), measures the magnitude of low frequency BOLD fluctuations, generally from 0.01 to 0.1 Hz.(99) fALFF measures the fractional strength (relative to the full spectrum) of BOLD fluctuations. ALFF is correlated with CBF,(100, 101) so this measure provides an alternative to supplement the pCASL analysis. This is a potentially important measure for brain stimulation, as fALFF/ALFF abnormalities have been reported in psychiatric disorders,(102-104) and fALFF in the subgenual cingulate gyrus has been shown to predict response to electroconvulsive therapy.(105) This analysis will use the BOLD resting data as above, except that frame censoring (scrubbing) will not be performed, since censoring can affect the frequencies in a run of BOLD-acquired MRI data. Each voxel's BOLD time series will be transformed into the frequency domain and the mean amplitude of the spectrum over the frequency range of 0.01–0.1 Hz will determine ALFF. fALFF for two bands (slow-4; 0.027-0.073 Hz; and slow-5, 0.01-0.027 Hz) will be calculated as the magnitude for that band over the magnitude of the full spectrum. This analysis will focus on the 10 mm diameter sphere under the site of stimulation. Alpha level for this analysis will be set at 0.017 (0.05/3), two-tailed.

Exploratory analyses, between measures: Exploratory analyses will also test for correlations between the three MRI measures, to provide a richer picture of iTBS effects. Lastly, we recognize that vertex stimulation, here being used as a control condition for dlPFC stimulation, may have some effects on brain networks, although it was selected to avoid the FPN. With some caveats (effect of order, since baseline is not counter-balanced), we can use baseline measures from the first MRI session (no preceding TMS session), to see if iTBS differences represent a change in the dlPFC-stimulated condition or the vertex-stimulated condition. An additional exploratory analysis will compare stimulation over the 'activated target' (2-back minus 1-back) versus the 'deactivated target' (1-back minus 2-back), based on how the target was selected.

Specific Aim 2: Demonstrate modulation of the effect of dlPFC iTBS by a cognitive task

Primary outcome measures:

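### Exploratory fALFF is specified on resting data already band-pass filtered to 0.01–0.1 Hz, so its full-spectrum denominator shrinks to roughly the pass-band

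*Combined protocol and SAP*

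**What the plan says.** All of the analysis text is in section 8.0 of the combined protocol and SAP, under Specific Aim 1.

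- **Resting pipeline** (analysis plan for primary outcome measure #2, BOLD connectivity). After the nuisance regressions the series is processed as: "followed by band pass filtering from 0.01 – 0.1 Hz, and then motion scrubbing".
- **Data for ALFF/fALFF** (exploratory analysis, amplitude of low frequency fluctuations). "This analysis will use the BOLD resting data as above, except that frame censoring (scrubbing) will not be performed". The reason given is that censoring can alter the frequency content of a run. The band-pass is not mentioned.
- **Definition of fALFF** (same paragraph). "fALFF measures the fractional strength (relative to the full spectrum) of BOLD fluctuations". The slow-4 (0.027–0.073 Hz) and slow-5 (0.01–0.027 Hz) values "will be calculated as the magnitude for that band over the magnitude of the full spectrum".
- **Definition of ALFF** (same paragraph). "the mean amplitude of the spectrum over the frequency range of 0.01–0.1 Hz will determine ALFF".
- **Purpose** (same paragraph). After noting that ALFF correlates with CBF, the plan says "so this measure provides an alternative to supplement the pCASL analysis".

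The only repetition time given for a BOLD scan is in section 6.3 (Visit 2), in the item on image acquisition: "BOLD-weighted fMRI (EPI, TR=800 ms, FOV=23, slice=2.4mm, 96x96 matrix) for the n-back task (8 minutes". The 10-minute resting scan listed next has no TR of its own.

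**The concern.** A ratio to the full spectrum needs the full spectrum. The series that the ALFF paragraph inherits has already lost almost everything outside 0.01–0.1 Hz, and the single exception it makes does not restore it. The denominator becomes roughly the sum of slow-5, slow-4 and the strip from 0.073 to 0.1 Hz. The quantity is then each band's share of the low-frequency range, not low-frequency strength relative to the whole spectrum.

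Two things follow. A general change in low-frequency amplitude after iTBS scales numerator and denominator together and largely cancels. A change in one band shifts the other band's share the opposite way, which could be read as a band-specific stimulation effect when none occurred there. The text also leaves room for two analysts to compute quite different measures under the same name, both tested at the stated alpha of 0.017.

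**Working it through.** The plan states no fALFF value, so there is no figure to reproduce. The one number attached to this analysis, alpha = 0.05/3 = 0.0167, is given rounded as 0.017 and is consistent.

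**Inputs from the documents**
- Pass-band: 0.1 − 0.01 = 0.09 Hz wide (section 8.0, primary outcome measure #2).
- Slow-4: 0.073 − 0.027 = 0.046 Hz. Slow-5: 0.027 − 0.01 = 0.017 Hz (section 8.0, ALFF paragraph). Remainder of the pass-band: 0.1 − 0.073 = 0.027 Hz.
- Resting scan: 10 minutes (section 6.3, Visit 2).

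**Assumptions**
- Resting TR = 0.8 s, carried over from the n-back scan. This gives 600/0.8 = 750 frames and a Nyquist frequency of 1/(2 × 0.8) = 0.625 Hz.
- Two amplitude spectra: flat, and 1/f plus white noise with amplitude √(0.03/f + 0.3).
- Two filters: an ideal 0.01–0.1 Hz band-pass, and an order-2 Butterworth band-pass run forward and backward.
- Amplitude changes of 20%, for illustration.

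**Formula.** fALFF = sum of amplitudes in the band / sum of amplitudes over all non-zero frequencies in the series used.

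**Step 1: what happens to the denominator.** The filter keeps 0.09/0.625 = 14.4% of the frequency range. For a flat spectrum, by bandwidth:
- Slow-4: 0.046/0.625 = 0.07 unfiltered, 0.046/0.09 = 0.51 filtered.
- Slow-5: 0.017/0.625 = 0.03 unfiltered, 0.017/0.09 = 0.19 filtered.

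**Step 2: a general 20% rise over 0.01–0.1 Hz, flat spectrum.**
- Unfiltered: 1.2/(1 + 0.2 × 0.144) = 1.2/1.0288 = 1.166, or +16.6%.
- Ideal filter: 1.2/1.2 = 1, or 0%.
- ALFF, as the mean amplitude over the same band, rises by the full 20% either way.

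**Step 3: a 20% rise in slow-4 only, flat spectrum, ideal filter.** On the discrete frequency grid (spacing 1/600 Hz) slow-4 holds 0.491 of the filtered total, close to the 0.51 from bandwidth.
- Slow-4: 1.2/(1 + 0.2 × 0.491) = 1.2/1.0982, or +9.3%.
- Slow-5: 1/1.0982, or −8.9%, although its amplitude has not changed.

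**All cases** (percent change in slow-4 / slow-5 fALFF):

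| 20% rise in | Series | Flat | 1/f plus white |
|---|---|---|---|
| all of 0.01–0.1 Hz | unfiltered | +16.6 / +16.6 | +15.2 / +15.2 |
| | ideal filter | 0.0 / 0.0 | 0.0 / 0.0 |
| | Butterworth | +3.3 / +3.3 | +2.6 / +2.6 |
| slow-4 only | unfiltered | +18.3 / −1.4 | +17.7 / −1.9 |
| | ideal filter | +9.3 / −8.9 | +9.7 / −8.6 |
| | Butterworth | +10.2 / −8.2 | +10.2 / −8.1 |
| slow-5 only | unfiltered | −0.6 / +19.3 | −1.2 / +18.6 |
| | ideal filter | −3.8 / +15.4 | −5.4 / +13.6 |
| | Butterworth | −3.2 / +16.1 | −4.6 / +14.5 |
| above 0.1 Hz only | unfiltered | −14.4 / −14.4 | −12.9 / −12.9 |
| | ideal filter | 0.0 / 0.0 | 0.0 / 0.0 |
| | Butterworth | −3.5 / −3.5 | −2.7 / −2.7 |

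**Step 4: sensitivity to TR.** If the resting TR were 2 s, Nyquist would be 1/(2 × 2) = 0.25 Hz and the filter would keep 0.09/0.25 = 36%. The unfiltered response to a general 20% rise would be 1.2/(1 + 0.2 × 0.36) = 1.2/1.072, or +11.9% (flat spectrum). The ideal-filter response stays at 0%.

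**The case against.** **The exception clause may simply be incomplete.** The authors name the full spectrum twice and drop scrubbing to protect the frequency content, so they may well intend an unfiltered series. That is plausible, and nothing shows a deliberate decision to filter. But the exception only makes sense if the resting pipeline otherwise applies, and no other text lifts the band-pass. The opening of section 8.0 allows slight differences in implementation. A change of denominator that moves slow-4 fALFF from about 0.07 to about 0.51 is not slight.

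**A reader might infer that fALFF could show no effect at all.** The working does not support that. A change confined to slow-4 or slow-5, the two bands the plan analyses, still appears: about +9 to +10% or +14 to +16% after filtering, against +18 to +19% unfiltered. Nor are the two bands locked in exact opposition. The strip from 0.073 to 0.1 Hz is 0.027/0.09 = 30% of a flat pass-band, so both can move together against it.

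**A reader might also infer that the back-up to the pCASL analysis would falsely read as null.** The documents do not support this either. The correlation with CBF is stated for ALFF, whose band equals the pass-band, so a general low-frequency rise would still register there. Only the fractional companion measure is blunted.

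**The exact zero and the 0.625 Hz limit are conditional.** This stands. The documents name no filter type and give no TR for the resting scan.

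**It is only exploratory.** This also stands, and it limits the weight of the point. It does not remove the contradiction.

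**Conclusion.** The plan is inconsistent as written. fALFF is defined against the full spectrum but specified on data from which most of that spectrum has been removed.

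- A general 20% change in low-frequency amplitude would appear as 0% (ideal filter) or about 3% (gradual filter) instead of 15 to 17%.
- A change confined to one band is attenuated. With an ideal filter it comes with an artefactual opposite shift of about −4 to −9% in the other band (about −3 to −8% with the gradual filter), against −1 to −2% when the full spectrum is used.

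These sizes rest on assumed spectra, assumed filters and a resting TR of 0.8 s. The loss of the denominator follows from the text alone, and the cancellation under an ideal filter depends on neither the TR nor the spectral shape.

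The scope is one exploratory measure. ALFF, every primary and secondary outcome, and the sample size are untouched.

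**What to change.** In the ALFF paragraph of section 8.0, extend the exception. State that fALFF is computed on the resting series before band-pass filtering and without frame censoring. State also that each band is divided by the amplitude over the whole unfiltered spectrum, up to the Nyquist frequency of the resting scan (0.625 Hz if TR is 0.8 s). Give the resting TR in section 6.3 so that this limit is fixed.

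The cost is one sentence, plus one extra output saved from the existing pipeline before the filter step. No new data are needed and no other analysis changes. It should be settled before the resting data are analysed, so that the choice of denominator cannot depend on the result.

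### The exploratory ALFF/fALFF analysis keeps all high-motion frames under a 60% cutoff justified by removing them, and names no mean-FD adjustment for the session contrast

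*Combined protocol and SAP*

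**What the plan says.** All the relevant text is in section 8.0 of the combined protocol and SAP, under Specific Aim 1.

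- **Connectivity (Primary outcome measure #2, Analysis Plan).** The plan censors "any frame with FD > 0.5 mm from the regression analysis described below, yielding a scrub ratio for each subject". The subject-level rule follows: "we will use 60% deleted frames as a cutoff for analyzable subjects". Its stated reason is that "as many as 60% of frames can be removed and still yield analyzable results".
- **Other motion control in the same pipeline.** Time courses are adjusted for "Linear trend, 6 motion parameters, their temporal derivatives, the quadratics of these 12 parameters, 5 components from the PCA of CSF", plus five white-matter components. In addition, "ICA-AROMA will be used to de-noise the data and remove additional, residual motion artifacts".
- **ALFF/fALFF (exploratory).** The same data are used, "except that frame censoring (scrubbing) will not be performed, since censoring can affect the frequencies in a run of BOLD-acquired MRI data". The region is a 10 mm diameter sphere at the stimulation site, tested two-sided at 0.017 (0.05/3). No ALFF-specific motion limit and no motion covariate are stated.
- **Global brain connectivity (exploratory).** The network ANCOVA does include mean FD, with age, as a covariate.

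**The concern.** The 60% rule tolerates a restless subject because the bad frames are thrown away. ALFF inherits the subject but not the disposal, so the stated reason for the cutoff does not carry over. The measure that loses frame censoring also has no stated group-level motion adjustment, though the plan uses one for a neighbouring exploratory measure.

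ALFF is an amplitude, so artefact that survives denoising tends to raise it. fALFF is a ratio of band to full-spectrum magnitude, so it can move in either direction. If subjects move more after one condition than another, part of the ALFF difference between sessions could be movement. ALFF is meant to supplement the pCASL perfusion analysis, so a motion-driven difference could wrongly appear to support or contradict the rCBF finding.

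**Working it through.** **1. The plan's own figure.** 0.05/3 = 0.0167, which rounds to the stated 0.017. No power calculation is attached to ALFF.

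**2. Frames at issue.** The resting scan lasts 10 minutes (section 6.2.2, MRI Image acquisition). TR is 800 ms for the n-back scan; I assume the same at rest.

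- Frames: 600 s / 0.8 s = 750.
- At the cutoff: 0.60 × 750 = 450 frames above 0.5 mm, leaving 300 for connectivity.
- ALFF would use all 750, including the 450.

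**3. Motion control that remains.** 6 parameters + 6 derivatives + 12 quadratics = 24 motion regressors, then 5 CSF and 5 white-matter components, then ICA-AROMA. Only the residual after these steps can affect ALFF.

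**4. Could a residual matter?** The documents give no residual size, so these are illustrative simulations of 750 frames.

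- With motion excursions and 24-parameter regression but no ICA-AROMA, ALFF was 6% above its motion-free value at about 19% of frames flagged, and 11% above at about 51%. Across scenarios, before or after regression, fALFF moved by -5% to +8%.
- With artefact placed directly in 30% of frames, ALFF inflation was 0.4% / 1.8% at a residual of 0.25 / 0.5 times the signal SD. At 1 times it was 7% to 23%, depending on the assumed shape of the artefact.

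So the effect on ALFF runs from negligible to material, and the documents do not say where in that range this study falls.

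**5. Effect on the session contrast.** The ALFF section does not name its test; I assume a paired two-sided t-test as elsewhere in Aim 1, with n = 40 (section 4.1) and alpha 0.017. Let δ be the mean between-session FD difference in SDs of that difference, and ρ the correlation of the ALFF difference with the FD difference. Both are assumptions. With no true iTBS effect:

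- standardised shift d = ρδ
- noncentrality = d√40
- critical value t(39) = 2.493

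| δ | ρ | d = ρδ | d√40 | False-positive rate | Simulated, unadjusted | Simulated, adjusted |
|---|---|---|---|---|---|---|
| 0 | 0.3 | 0 | 0 | 1.7% | 1.9% | 1.7% |
| 0 | 0.5 | 0 | 0 | 1.7% | 1.4% | 1.5% |
| 0.25 | 0.3 | 0.075 | 0.474 | 2.9% | 3.1% | 1.7% |
| 0.25 | 0.5 | 0.125 | 0.791 | 5.3% | 5.4% | 1.5% |
| 0.5 | 0.3 | 0.150 | 0.949 | 7.1% | 6.8% | 1.6% |
| 0.5 | 0.5 | 0.250 | 1.581 | 19.4% | 18.3% | 1.7% |

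The simulated columns use 8,000 runs per row. The adjusted column regresses the paired difference on the FD difference and tests the intercept. A separate simulation gave 6.7% / 19.9% unadjusted and 1.6% / 1.4% adjusted for the last two rows.

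With δ = 0 the error rate stays nominal even at ρ = 0.5. With ρ = 0 it stays nominal whatever the FD difference. Both conditions are needed for bias.

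**The case against.** Most of the opposing case stands, and it limits the point.

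- **Denoising remains.** Only scrubbing is dropped. A reader might infer that movement as such inflates ALFF here. The documents do not support that: three layers of motion and noise control stay in place, and the size of what they leave is unknown. For fALFF even the direction is not fixed. However, the plan applies scrubbing as well as these steps for connectivity, so it does not rely on them alone there.
- **Within-subject design.** A reader might also infer that a motion artefact will pass for an iTBS effect. A subject who moves alike in each session contributes similarly to both sides of the contrast, and chance differences add noise without bias. Nothing in the documents shows movement that depends on condition. Counterbalancing (section 4.4) deals with order, though, not with movement that a condition itself provokes. Section 9.3.1.3 lists scalp pain near the stimulation site as common, and dlPFC and vertex are different sites, so a difference is possible but not shown.
- **Reason for not censoring.** The plan's reason, that censoring alters the frequencies, is sound against deleting frames. It does not argue against a motion covariate. Interpolating flagged frames looks like a way round it but brings its own motion-dependent bias. In simulation, interpolation alone raised slow-4 fALFF by about 15% at 30% flagged and about 34% at 59%. It raised ALFF by 12% at 30% flagged once white noise was added.
- **Importance.** ALFF is labelled exploratory, is not a listed primary or secondary outcome, and no decision rule uses it to confirm rCBF.

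**Conclusion.** The point holds as a minor gap in an exploratory analysis. ALFF and fALFF keep every frame above 0.5 mm, inherit a cutoff whose only stated reason is frame removal, and have no stated mean-FD adjustment. Under assumed between-session FD differences of 0 / 0.25 / 0.5 SD and ALFF-motion correlations of 0.3 to 0.5, the false-positive rate is about 2% / 3-5% / 7-20% against a nominal 1.7%. Adjustment brings it to about 1.4-1.9%. These figures depend on the assumed FD difference and correlation, n = 40, a paired test and a linear relation between the ALFF and FD differences. They show what could happen, not that conditions will differ in movement. The primary outcomes are unaffected.

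**What to change.** In the ALFF section of 8.0:

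1. Adjust the paired between-session ALFF and fALFF differences for the within-subject difference in mean FD. Test the intercept with the FD difference left uncentred, so that it estimates the contrast at equal movement. Centring would restore the unadjusted mean.
2. Report FD and the proportion of frames above 0.5 mm by session and condition.
3. Do not carry the 60% cutoff over as if frames had been removed. Repeat the analysis excluding high-motion sessions, under a rule fixed in advance, as a sensitivity check.
4. Do not prescribe interpolation, for the reason given above.

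The cost is SAP wording, one degree of freedom and possibly a few fewer sessions in the sensitivity analysis. FD is already computed, and mean FD is already a covariate in the connectivity ANCOVA. Precision changes little: in large samples the standard error changes by a factor of about √[(1 + δ²)(1 − ρ²)]. At δ = 0.5 this is √(1.25 × 0.91) = 1.07 for ρ = 0.3 and √(1.25 × 0.75) = 0.97 for ρ = 0.5.

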3.0 Study design

The study is a within-subjects design that will expose subjects to three TMS/TBS sessions, with each followed by an MRI session. The first MRI session, without TMS, will obtain baseline

measurements of FPN activation (providing the target for iTBS stimulation – see below), resting state connectivity and resting state cerebral perfusion. The subsequent 3 MRI sessions will occur in a counterbalanced order, acquiring the same imaging sequence, and following one of three iTBS sessions: 1) To dIPFC, without a concurrent task; 2) to vertex, without any concurrent task, and 3) To dIPFC, while subjects perform an n-back task.

Overview of experimental sessions

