6.3.3 TMS session: We will deliver iTBS, which has been shown to increase cortical excitability,(30) using 3 pulses of stimulation at 50 Hz, repeated every 200 ms, for 2 sec trains, repeated every 10 sec, giving a total of 600 pulses in 190 sec. Stimulation will be delivered at 80% of AMT, which is within consensus recommendations for safety,(80) and used in published work.(81)

In counter-balanced order, subjects will receive one of three iTBS sessions on each of the 3 days: 1) Vertex stimulation and subjects will be instructed to maintain gaze on a fixation screen and rest; 2) dlPFC stimulation (from neuronavigated target described above, subjects will be instructed to maintain gaze on a fixation screen and rest; or 3) dlPFC stimulation augmented with an n-back task. A computer screen will display an n-back task, using the 2-back condition. Letters will appear for 0.5 sec every 2 seconds, and presentation will be synchronized with the iTBS stimulation, which will occur 0.5 sec before the onset of every 5th letter. Actual parameters may differ slightly when delivered in the experiment.

6.3.4 MRI session: MRI sessions will be identical to Visit #2. The MRI will follow immediately after the iTBS TMS session.

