To examine state-dependency and modulation of iTBS effects by task, we will contrast MRI measures following iTBS applied to the dlPFC while subjects perform the n-back with MRI measures following iTBS compared to when they are in an unconstrained, resting state. The general analysis plan will use the same work-up of the imaging data as described above, the only difference being the MRI sessions that are compared with each other. Although directions of change are difficult to predict, we are predicting increasing activity as has been reported for iTBS applied during a deep encoding memory paradigm and not observed during shallow-encoding.(106) However, it is possible that cortex may become more efficient and less activation may be seen. The following primary hypotheses will be tested:

Primary outcome #1, BOLD activation: 2-back minus 1-back BOLD activation, voxelwise in FPN
(H2.1) For dlPFC stimulation during performance of a n-back task, compared to dlPFC
stimulation in a resting, unconstrained mental state, FPN activation to the n-back task will be
greater. For this analysis, the region of interest will be the FPN taken from the activation mask,
as described above. For a secondary measure to test H2.1, we will examine whole brain
activation, since change may occur outside this region of interest.

Primary outcome measure #2, BOLD connectivity: FPN connectivity to dlPFC iTBS stimulation
target

(H2.2) For dlPFC stimulation during performance of a n-back task, compared to dlPFC
stimulation in a resting, unconstrained mental state, connectivity with the dlPFC site of
stimulation will increase. For this analysis, the region of primary interest will be connectivity to
site of stimulation.

Primary outcome measure #3, rCBF at stimulation target

(H2.3) For dlPFC stimulation during performance of a n-back task, compared to dlPFC
stimulation in a resting, unconstrained mental state, resting perfusion at stimulation site will
increase. The primary region of interest will be the site of stimulation, and secondary analyses
will focus on the FPN, defined by n-back activation.

Specific Aim 3: Demonstrate improvement in cognitive control with iTBS, modulated by cognitive task during stimulation

Primary outcome measure: accuracy to 2-back

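### Aim 2 and H3.2 cannot isolate modulation of the iTBS effect by the task, because no control stimulation is given during the task

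*Combined protocol and SAP*

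**What the plan says.** Sections 3.0 and 6.3.3 define three stimulation sessions in counterbalanced order: vertex at rest, dlPFC at rest, and dlPFC during an n-back task. The control session is "to vertex, without any concurrent task" (section 3.0), and section 6.3.3 repeats this: "Vertex stimulation and subjects will be instructed to maintain gaze on a fixation screen and rest". In the combined session, "A computer screen will display an n-back task, using the 2-back condition". On timing, section 6.3.4 says "The MRI will follow immediately after the iTBS TMS session".

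Each scan visit lists three functional scans (section 6.2.2, MRI Image acquisition): first the n-back for 8 minutes, then a "BOLD-weighted resting state scan for 10 minutes to obtain data for functional connectivity analyses", then perfusion imaging.

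In section 8.0 the title of Specific Aim 2 is "Demonstrate modulation of the effect of dlPFC iTBS by a cognitive task". Its lead sentence begins "To examine state-dependency and modulation of iTBS effects by task, we will contrast MRI measures following iTBS applied to the dlPFC while subjects perform". It goes on to name an n-back as the task and dlPFC iTBS at rest as the comparator. H2.1 to H2.3 apply this comparison to n-back activation, connectivity and perfusion, and H3.2 applies it to 2-back accuracy. The Aim 3 title also speaks of modulation by the task, and the synopsis says the study will examine how TBS and mental state interact.

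The only related caveat is under the exploratory between-measures analyses in section 8.0. It says vertex stimulation may itself have effects, and it offers the baseline scan as a reference: "With some caveats (effect of order, since baseline is not counter-balanced". An after-effect of the 2-back block is not mentioned.

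**The concern.** To say that the task modulates the iTBS effect is to claim an interaction: the effect of dlPFC stimulation relative to control stimulation is different under task than at rest. That needs control stimulation in both states, and the plan has it only at rest.

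The two sessions compared in Aim 2 and H3.2 have the same stimulation site and differ in whether a 2-back was performed just before scanning. Warm-up, priming, fatigue or residual activation from that block could produce a difference with no interaction at all, or could offset a real one.

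State-dependence of iTBS is the study's broad hypothesis, and section 9.4 says the results will be used to improve TMS treatment by controlling mental state. A task after-effect reported as modulation would be carried into that work. Section 1.1 itself says that showing a combination to beat one of its components has little scientific value. Without a task control, these contrasts show no more than that.

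**Working it through.** **Inputs.** Three stimulation sessions and one no-TMS baseline scan (sections 3.0, 6.3.3). iTBS lasts 190 s and letters appear every 2 s (6.3.3). The n-back scan takes 8 minutes and is listed first (6.2.2). 40 analysable subjects (4.1). Alpha for each primary MRI measure is 0.017 (8.0). No alpha is stated for H3.2, so 0.05 is assumed. The plan gives no effect size, SD or power for these contrasts.

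**The plan's own figure.** 0.05/3 = 0.0167, which rounds to the stated 0.017.

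**Estimability.** Write each session mean as intercept + site (dlPFC versus vertex) + task + site × task:

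| Session | Intercept | Site | Task | Site × task |
|---|---|---|---|---|
| Vertex, rest | 1 | 0 | 0 | 0 |
| dlPFC, rest | 1 | 1 | 0 | 0 |
| dlPFC, 2-back | 1 | 1 | 1 | 1 |

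- The rank is 3 for 4 parameters.
- Aim 1 and H3.1: row 2 − row 1 = (0, 1, 0, 0). The site effect at rest is estimable.
- Aim 2 and H3.2: row 3 − row 2 = (0, 0, 1, 1), which is task + interaction. The sum is estimable; (0, 0, 1, 0) and (0, 0, 0, 1) are not.
- Adding the baseline scan also requires a term for any stimulation versus none. The rank becomes 4 of 5, and the interaction is still not estimable.

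**Task exposure before each outcome.** 190 s / 2 s per letter = 95 letters; 190/60 = 3.2 minutes. This assumes that the task runs for the length of the stimulation and that scans follow the listed order.

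| Outcome | n-back that visit, dlPFC + task | n-back that visit, dlPFC at rest |
|---|---|---|
| n-back scan (H2.1, H3.2) | 3.2 min | 0 min |
| Resting BOLD (H2.2) | 8 + 3.2 = 11.2 min | 8.0 min |

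Perfusion (H2.3) is listed after resting BOLD, so the 8-minute n-back precedes it in every session too. H2.1 and H3.2 are therefore the most exposed. The 2-back minus 1-back subtraction in H2.1 removes whatever affects both loads equally. The pre-scan block is 2-back only, however, so a load-specific after-effect remains. H3.2 has no such subtraction.

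**Illustration with assumed effect sizes.** Suppose there is no modulation and the task after-effect is d SDs of the paired difference. For a two-sided paired t-test with n = 40, the rejection probability is 1 − F(c) + F(−c), where F is the noncentral t distribution with 39 df and noncentrality d√40, and c is the two-sided critical value.

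| d | d√40 | alpha 0.05 (H3.2, assumed) | alpha 0.017 (single-region test, H2.3) |
|---|---|---|---|
| 0.1 | 0.63 | 9.5% | 3.9% |
| 0.2 | 1.26 | 23.5% | 12.2% |
| 0.3 | 1.90 | 45.7% | 28.8% |
| 0.4 | 2.53 | 69.4% | 52.0% |

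These rates do not describe the voxelwise FDR tests of H2.1 and H2.2.

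**The case against.** The strongest reply is that the hypotheses as written are simple contrasts. H2.1 to H2.3 and H3.2 ask whether stimulation with the task differs from stimulation at rest, and they test that validly. For H3.2 the plan gives a practical reason: to learn whether combining TMS with a task helps or harms performance. For that question the task's own contribution belongs in the estimate. All of this stands. The fault is in the interpretation carried by the titles, the synopsis and the lead sentence. Section 9.4 also states the broad hypothesis as TMS-induced changes being enhanced, which is an interaction claim.

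A second reply is that the after-effect may be small. The TMS suite is across the hall from the magnet, and positioning and localizer scans come before the n-back. The documents cite up to 60 minutes of persistence for iTBS and nothing comparable for a 3-minute task. The exact task length is inferred, and section 6.3.3 allows parameters to vary slightly. This too stands: size and direction are unknown, and the rates above are only a sensitivity range. If the paired tests for H3.2 are run only after a significant overall ANCOVA (the plan calls them post-hoc but states no gate), a simulation with vertex equal to dlPFC at rest gives about 6, 17, 37 and 64% in place of 10, 24, 46 and 69%. The identification problem does not depend on any of these figures.

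Third, mock-scanner practice, the baseline n-back and counterbalancing limit practice effects. They deal with general learning and session order. The 2-back block always accompanies the same condition, so they cannot remove its immediate after-effect.

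Finally, this is an exploratory study in healthy volunteers. That is a good reason not to add a session, but it does not license a conclusion the design cannot reach.

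**Conclusion.** The concern holds. H2.1 to H2.3 and H3.2 each estimate task after-effect plus stimulation-by-task interaction, and no analysis of the planned sessions separates the two. A positive result would be compatible with modulation but would not establish it. A null result would not rule it out, since the two parts could cancel.

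This rests only on the list of sessions and needs no assumption about effect size. How far it would mislead in practice is unknown; the illustration runs from about 10% to 69% false attribution for H3.2 across assumed after-effects of 0.1 to 0.4 SD. Exposure is greatest for H2.1 and H3.2 and smaller for H2.2 and H2.3. Aim 1 and H3.1 are not affected. The wording should be changed; the tests can stay.

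**What to change.** Keep the design and the contrasts.

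1. Reword the Aim 2 and Aim 3 titles, the interaction statement in the synopsis and the lead sentence of Aim 2 in section 8.0. H2.1 to H2.3 and H3.2 should be described as the combined effect of dlPFC iTBS with concurrent 2-back versus dlPFC iTBS at rest.
2. Add to section 8.0:

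> No control stimulation is given during the task. This contrast therefore includes the direct after-effect of performing the 2-back before the scan. A difference will not be reported as an interaction with, or modulation of, the iTBS effect.

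3. Note there that the limitation is greatest for H2.1 and H3.2 and smaller for H2.2 and H2.3.

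The cost is a narrower headline claim, with no change to visits, sample size or tests.

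A vertex session with the 2-back would make the interaction estimable (rank 4 of 4), but it adds a visit and loses precision. With equal variances and correlations across sessions, the interaction has twice the variance of one paired difference. At n = 40, alpha 0.017 and 80% power, the detectable effect rises from 0.53 to 0.53 × √2 = 0.75 SD of a paired difference, and about 78 subjects would be needed to detect 0.53. Rewording is the proportionate change here.
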